## 9. Balance Assessment

**Action report links:**

Optum: <https://bwh-dope.aetion.com/projects/details/1484/results/64541/result/0>

Marketscan: <https://bwh-dope.aetion.com/projects/details/1481/results/64542/result/0>

Medicare: <https://bwh-dope.aetion.com/projects/details/1483/results/64543/result/0>

Date conducted: 1/19/2021

After review of initial feasibility and power analyses, complete creation of the remaining covariates from Section 6.2. Again, using the dummy outcome of a 90-day gap in database enrollment, complete a 1:1 PS-matched analysis. The PS should include the complete list of covariates.

- Provide plot of PS distributions stratified by treatment group.

Note- Please refer to **Appendix B**.

- Report covariate balance after matching.

Note- For Table 1, please refer to **Appendix B**.

- Report reasons for censoring by treatment group.

|  | Overall | Referent | Exposure |
|--|---------|----------|----------|
|--|---------|----------|----------|

|                                                                                                                               |                |                |                |
|-------------------------------------------------------------------------------------------------------------------------------|----------------|----------------|----------------|
| Dummy outcome                                                                                                                 | 67 (0.94%)     | 25 (0.70%)     | 42 (1.18%)     |
| Death                                                                                                                         | 103 (1.44%)    | 49 (1.37%)     | 54 (1.51%)     |
| Start of an additional exposure                                                                                               | 232 (3.25%)    | 175 (4.90%)    | 57 (1.60%)     |
| End of index exposure                                                                                                         | 4,701 (65.84%) | 2,202 (61.68%) | 2,499 (70.00%) |
| Specified date reached                                                                                                        | 857 (12.00%)   | 424 (11.88%)   | 433 (12.13%)   |
| End of patient enrollment                                                                                                     | 425 (5.95%)    | 198 (5.55%)    | 227 (6.36%)    |

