# Appendix B

The c-statistics for the propensity score model, pre-matching was 0.938. The postmatching c-statistic was 0.684.

[figure not shown]
[figure not shown]
[figure not shown]

The c-statistics for the propensity score model, pre-matching was 0.848. The postmatching c-statistic was 0.572.

The c-statistics for the propensity score model, pre-matching was 0.874. The postmatching c-statistic was 0.566.

AFTER PS MATCHING

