| Hypertension: 1 inpatient or 2 outpatient claims within 365 days; n (%)            | 588 (39.9%)          | 996 (35.8%)         | 0.08      | 974 (39.5%)          | 1,599 (41.3%)       | -0.04     | 2,258 (45.3%)        | 1,402 (41.2%)     | 0.08      | 3,820 (42.8%)        | 3,997 (39.7%)       | 0.06      |
| Hyperlipidemia v2; n (%)                                                           | 508 (34.5%)          | 964 (34.6%)         | 0.00      | 705 (28.6%)          | 1,203 (31.1%)       | -0.05     | 1,995 (40.0%)        | 1,423 (41.8%)     | -0.04     | 3,208 (36.0%)        | 3,590 (35.7%)       | 0.01      |
| Edema; n (%)                                                                       | 243 (16.5%)          | 444 (16.0%)         | 0.01      | 335 (13.6%)          | 550 (14.2%)         | -0.02     | 789 (15.8%)          | 506 (14.9%)       | 0.02      | 1,367 (15.3%)        | 1,500 (14.9%)       | 0.01      |
| Renal Dysfunction (non-diabetic) v2; n (%)                                         | 213 (14.5%)          | 407 (14.6%)         | 0.00      | 307 (12.5%)          | 486 (12.5%)         | 0.00      | 916 (18.4%)          | 580 (17.0%)       | 0.04      | 1,436 (16.1%)        | 1,473 (14.6%)       | 0.04      |
| Occurrence of acute renal disease v2; n (%)                                        | 86 (5.8%)            | 202 (7.3%)          | -0.06     | 159 (6.5%)           | 265 (6.8%)          | -0.01     | 513 (10.3%)          | 284 (8.3%)        | 0.07      | 758 (8.5%)           | 751 (7.5%)          | 0.04      |
| Occurrence of chronic renal insufficiency; n (%)                                   | 87 (5.9%)            | 124 (4.5%)          | 0.06      | 84 (3.4%)            | 113 (2.9%)          | 0.03      | 359 (7.2%)           | 197 (5.8%)        | 0.06      | 530 (5.9%)           | 434 (4.3%)          | 0.07      |

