| HAS-BLED Score (ICD-9 and ICD-10), 180 days                                       |                     |                     |             |                     |                     |               |                 |                 |              |                   |                   |         |         |      |
| ...mean (sd)                                                                      | 2.01 (0.69)         | 1.99 (0.71)         | 0.03        | 1.88 (0.70)         | 1.88 (0.68)         | 0.00          | 2.34 (0.79)     | 2.36 (0.77)     | -0.03        | 2.16 (0.75)       | 2.07 (0.72)       | 0.00    |         |      |
| N of Generic name drugs                                                           |                     |                     |             |                     |                     |               |                 |                 |              |                   |                   |         |         |      |
| ...mean (sd)                                                                      | 13.81 (14.14)       | 12.17 (14.72)       | 0.11        | 11.84 (10.98)       | 10.94 (11.84)       | 0.08          | 18.87 (18.89)   | 17.63 (18.34)   | 0.07         | 16.09 (16.30)     | 13.54 (15.09)     | 0.00    |         |      |
| N of Brand name drugs                                                             |                     |                     |             |                     |                     |               |                 |                 |              |                   |                   |         |         |      |
| ...mean (sd)                                                                      | 1.91 (3.43)         | 3.26 (4.17)         | -0.35       | 2.10 (3.31)         | 3.10 (3.40)         | -0.30         | 3.01 (5.24)     | 4.06 (5.03)     | -0.20        | 2.58 (4.51)       | 3.47 (4.22)       | 0.00    |         |      |
| Use of clopidogrel; n (%)                                                         | 12 (0.8%)           | ** (0.3%)           | 0.07        | 18 (0.7%)           | 16 (0.4%)           | 0.04          | 175 (3.5%)      | 113 (3.3%)      | 0.01         | 205 (2.3%)        | #VALUE!           | #VALUE! |         |      |

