| Treating prescriber - Other; n (%)                                                                    | 1,449 (98.4%) | 2,693 (96.8%) | 0.10          | 2,303 (93.5%) | 3,562 (91.9%) | 0.06    | 4,710 (94.5%) | 3,212 (94.3%) | 0.01          | 8,462 (94.9%) | 9,467 (94.1%) | 0.04    |
| Alpha blockers; n (%)                                                                                 | 73 (5.0%)     | 146 (5.2%)    | -0.01         | 95 (3.9%)     | 155 (4.0%)    | -0.01   | 373 (7.5%)    | 278 (8.2%)    | -0.03         | 541 (6.1%)    | 579 (5.8%)    | 0.01    |
| CHADS2 VASc score, 180 days, V                                                                        |               |               |               |               |               |         |               |               |               |               |               |         |
| ...mean (sd)                                                                                          | 1.73 (1.38)   | 1.29 (1.12)   | 0.35          | 1.73 (1.43)   | 1.08 (1.06)   | 0.52    | 2.01 (1.68)   | 1.45 (1.21)   | 0.38          | 1.89 (1.57)   | 1.26 (1.13)   | 0.00    |
| Use of Prasugrel; n (%)                                                                               | 0 (0.0%)      | ** (0.1%)     | -0.04         | 0 (0.0%)      | ** (0.1%)     | -0.04   | 0 (0.0%)      | 0 (0.0%)      | #DIV/0!       | 0 (0.0%)      | #VALUE!       | #VALUE! |
| Use of Loop Diuretics+other diuretics+other hypertension drugs; n (%)                                 |               |               |               |               |               |         |               |               |               |               |               |         |
| Commercial vs Medicare Advantage- BusinessType                                                        | 154 (10.5%)   | 275 (9.9%)    | 0.02          | 241 (9.8%)    | 344 (8.9%)    | 0.03    | 899 (18.0%)   | 523 (15.4%)   | 0.07          | 1,294 (14.5%) | 1,142 (11.3%) | 0.10    |
| Code - CORRECT ONE - OPTUM                                                                            |               |               |               |               |               |         |               |               |               |               |               |         |

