| H2 receptor antagonist; n (%)                                              | 15 (3.1%)     | 21 (4.3%)   | -0.06       | 47 (3.4%)     | 49 (3.5%)     | -0.01   | 128 (7.5%)    | 139 (8.2%)    | -0.03       | 190 (5.3%)    | 209 (5.9%)    | -0.03   |
| Vitamin K therapy; n (%)                                                   | 0 (0.0%)      | 0 (0.0%)    | #DIV/0!     | 0 (0.0%)      | 0 (0.0%)      | #DIV/0! | 0 (0.0%)      | 0 (0.0%)      | #DIV/0!     | 0 (0.0%)      | 0 (0.0%)      | #DIV/0! |
| Number of INR (prothrombin) tests ordered                                  |               |             |             |               |               |         |               |               |             |               |               |         |
| ...mean (sd)                                                               | 0.80 (1.89)   | 0.53 (1.24) | 0.17        | 0.68 (1.73)   | 0.50 (1.11)   | 0.12    | 0.51 (1.10)   | 0.49 (1.06)   | 0.02        | 0.62 (1.49)   | 0.50 (1.11)   | 0.00    |
| Treating prescriber - Cardiologist; n (%)                                  | 299 (61.0%)   | 313 (63.9%) | -0.06       | 871 (63.1%)   | 868 (62.9%)   | 0.00    | 880 (51.8%)   | 902 (53.1%)   | -0.03       | 2050 (57.4%)  | 2083 (58.3%)  | -0.02   |
| Treating prescriber - Primary Care Physician                               | 415 (84.7%)   | 407 (83.1%) | 0.04        | 600 (43.4%)   | 636 (46.3%)   | -0.05   | 642 (37.8%)   | 637 (37.5%)   | 0.01        | 1657 (46.4%)  | 1680 (47.1%)  | -0.01   |
| Treating prescriber - Other; n (%)                                         | 474 (96.7%)   | 476 (97.1%) | -0.02       | 1,287 (93.2%) | 1,288 (93.3%) | 0.00    | 1,613 (94.9%) | 1,617 (95.2%) | -0.01       | 3374 (94.5%)  | 3381 (94.7%)  | -0.01   |
| Alpha blockers; n (%)                                                      | 30 (6.1%)     | 21 (4.3%)   | 0.08        | 54 (3.9%)     | 56 (4.1%)     | -0.01   | 123 (7.2%)    | 125 (7.4%)    | -0.01       | 207 (5.8%)    | 202 (5.7%)    | 0.00    |
| CHA2DS2 VASc score, 180 days, V                                            |               |             |             |               |               |         |               |               |             |               |               |         |

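### The CHA2DS2-VASc row in Appendix B does not agree with its own component rows and appears to be measured differently by arm, yet Section 9 puts it in the propensity score

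*Combined protocol and SAP*

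**What the plan says.** Appendix B gives the score as "CHADS2 VASc score, 180 days, V" in the unmatched table and "CHA2DS2 VASc score, 180 days, V" in the matched table, with means and SDs only. No weights and no code list for the score appear in the documents. The bleeding score in the same table is labelled "HAS-BLED Score (ICD-9 and ICD-10), 180 days"; the CHA2DS2-VASc row carries no ICD note. The main hypertension row is "Hypertension: 1 inpatient or 2 outpatient claims within 365 days", so its stated window is longer than the score's.

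Section 9 says of the balance step: "The PS should include the complete list of covariates". Section 6.2 points to Table 1 in Appendix B for that list. After matching, the score's standardized differences are -0.03, -0.01 and -0.01. The comparative analysis entries in Section 13 are still blank.

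**The concern.** The mean of an additive score equals the weighted sum of its component prevalences, however the components overlap within patients. Table 1 prints the main components, so the score can be checked against them. If the reported mean is below the sum, either the score or the component rows are wrong. If the score differs between arms while the components do not, the error differs by treatment.

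A PS covariate with such an error asks the match to remove a difference that may not exist. That can discard usable pairs and change which patients are compared. Matching keeps 3,570 of 8,919 warfarin users and 3,570 of 10,063 apixaban users, so overlap is already limited.

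**Working it through.** **The plan's own figures.** The standardized difference is (m1 - m2)/sqrt((s1² + s2²)/2).
- Optum: (1.73 - 1.29)/sqrt((1.38² + 1.12²)/2) = 0.350
- MarketScan: (1.73 - 1.08)/sqrt((1.43² + 1.06²)/2) = 0.516
- Medicare: (2.01 - 1.45)/sqrt((1.68² + 1.21²)/2) = 0.383

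These match the printed 0.35, 0.52 and 0.38, and the n-weighted pooled means (1.886 and 1.263) match the printed 1.89 and 1.26. The row is consistent with itself. The one exception is the pooled standardized difference, printed as 0.00, where its own means and SDs give 0.46.

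**Assumption.** Standard weights: 1 each for female sex, age 65-74, heart failure, hypertension, diabetes and vascular disease; 2 each for age 75 or over and stroke.

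**Inputs.** Counts are from Table 1 in Appendix B. For Medicare apixaban (n = 3,406): female 1,835; age 65-74, 998; over 75, 700; heart failure 506; diabetes 694; hypertension 1,402. The four age bands add to 3,406 (852 + 856 + 998 + 700), so no patient is lost at the age-75 boundary.

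- Age and sex: (1,835 + 998 + 2 × 700)/3,406 = 1.243
- Plus heart failure and diabetes: + (506 + 694)/3,406 = 1.595
- Plus hypertension: + 1,402/3,406 = 2.007

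The same sums elsewhere:

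| Arm | Age, sex | + heart failure, diabetes | + hypertension | Reported |
|---|---|---|---|---|
| Optum warfarin | 0.865 | 1.111 | 1.511 | 1.73 |
| Optum apixaban | 0.861 | 1.119 | 1.477 | 1.29 |
| MarketScan warfarin | 0.555 | 0.791 | 1.186 | 1.73 |
| MarketScan apixaban | 0.569 | 0.801 | 1.214 | 1.08 |
| Medicare warfarin | 1.203 | 1.593 | 2.046 | 2.01 |
| Medicare apixaban | 1.243 | 1.595 | 2.007 | 1.45 |
| Medicare warfarin, matched | 1.202 | 1.588 | 2.044 | 1.55 |
| Medicare apixaban, matched | 1.197 | 1.615 | 2.075 | 1.56 |

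Stroke and vascular disease would add to every sum.

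**Without hypertension.** Medicare apixaban (1.595 against 1.45) and both matched Medicare arms (1.588 against 1.55; (918 + 427 + 2 × 344 + 304 + 407)/1,699 = 1.615 against 1.56) still exceed the reported means. Optum and MarketScan apixaban do not.

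**Weights.** With every weight set to 1 and hypertension included, the apixaban sums are 1.37, 1.19 and 1.80, all above the reported 1.29, 1.08 and 1.45. With every weight set to 1 and hypertension left out, Medicare apixaban gives (1,835 + 998 + 700 + 506 + 694)/3,406 = 1.39, which is below 1.45. The result without hypertension therefore needs the weight of 2 for age 75 or over.

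**Between arms.** Warfarin minus apixaban, five-component sum: Optum 1.511 - 1.477 = 0.034; MarketScan 1.186 - 1.214 = -0.028; Medicare 2.046 - 2.007 = 0.039. Reported score: 0.44, 0.65 and 0.56. Before matching, the standardized differences for sex, heart failure, hypertension, diabetes and stroke are at most 0.08, and for the age bands at most 0.10.

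**Weight in the match.** Under a normal approximation, the score's discrimination alone is Φ((m1 - m2)/sqrt(s1² + s2²)) = 0.60, 0.64 and 0.61. Heparin or low-molecular-weight heparin alone gives 0.5 + (0.571 - 0.044)/2 = 0.76 in Optum and 0.5 + (0.421 - 0.045)/2 = 0.69 in Medicare. For the full models, the first c-statistic listed is "pre-matching was 0.938"; the others are 0.848 and 0.874.

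**The case against.** The strongest objection is that the printed rows are not shown to be the score's components. Optum and MarketScan warfarin lie above their sums, by 0.22 and 0.54 on the five components. A score that only missed codes could not do that. This stands: a reader might infer that the score under-counts throughout, and two of the six unmatched arms contradict it.

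The hypertension objection also stands for two databases. Counting half the listed hypertension gives 1.477 - 0.179 = 1.298 for Optum apixaban against 1.29, and 1.214 - 0.2065 = 1.008 for MarketScan apixaban against 1.08. Their shortfalls therefore depend on the 365-day row. Medicare apixaban on the same test is 1.80 against 1.45.

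A reader might infer that ICD-10 codes are missing, so that pairs are formed on coding era instead of risk. The documents do not support that. No index dates or coding era are reported by arm, many other rows also lack an ICD note, and Appendix A describes a systematic ICD-9 to ICD-10 conversion. Heart failure, hypertension and diabetes are balanced after matching, with standardized differences of at most 0.05.

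Table assembly is another possible cause. The unmatched Medicare score entries, 2.01 (1.68) and 1.45 (1.21), also appear in the Medicare columns of the immobilization row. A copying error in that table would not explain the matched Medicare means, which are different numbers and also fall short.

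A reader might also infer that the match is driven by an artefact. No PS coefficients and no PS without the score are reported, and heparin use is a stronger discriminator in Optum and Medicare.

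**Conclusion.** The inconsistency is real. It is firmest in Medicare: a shortfall of 0.15 for unmatched apixaban and 0.04 to 0.05 in the matched arms without hypertension, and 0.56 for unmatched apixaban with it (2.01 - 1.45). These figures assume the standard weights and that the heart failure and diabetes rows feed the score. In Optum and MarketScan apixaban the shortfalls of 0.19 and 0.13 hold only if the 365-day hypertension row applies.

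The between-arm finding needs less. In all three databases nearly balanced components cannot produce score differences of 0.44 to 0.65, so the score appears to be measured differently by arm. Incomplete ICD-10 coding and a table-assembly error are both possible; neither is established. Section 9 places the score in the PS, so it influences the match and may cost overlap. By how much cannot be told from the documents.

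**What to change.** Before the comparative analyses, state the score's weights, look-back and code lists, and check its mean in each arm against the component rows. Then either correct the score or drop it from the PS; age, sex, heart failure, hypertension, diabetes, stroke and peripheral vascular disease are already listed as covariates. Refit the PS, re-match, and reissue the matched N, balance table, c-statistics and the Section 10 power tables. Correct the pooled standardized difference at the same time.

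The cost is one re-run with no new data. The matched N may change and power with it, since Section 10 derives expected events from it (7,140 × 13.74/1,000 = 98.1).

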# Appendix B

| PS-matched                                                                        |                      |                     |           |                      |                     |           |                      |                     |           |                      |                     |           |
|-----------------------------------------------------------------------------------|----------------------|---------------------|-----------|----------------------|---------------------|-----------|----------------------|---------------------|-----------|----------------------|---------------------|-----------|
|                                                                                   | Optum                |                     |           | MarketScan           |                     |           | Medicare             |                     |           | POOLED               |                     |           |
| Variable                                                                          | Reference - Warfarin | Exposure - Apixaban | St. Diff. | Reference - Warfarin | Exposure - Apixaban | St. Diff. | Reference - Warfarin | Exposure - Apixaban | St. Diff. | Reference - Warfarin | Exposure - Apixaban | St. Diff. |
| Number of patients                                                                | 490                  | 490                 |           | 1,381                | 1,381               |           | 1,699                | 1,699               |           | 3,570                | 3,570               |           |
| Age                                                                               |                      |                     |           |                      |                     |           |                      |                     |           |                      |                     |           |
| ...mean (sd)                                                                      | 57.18 (14.30)        | 57.47 (14.12)       | -0.02     | 51.78 (12.29)        | 51.77 (12.07)       | 0.00      | 62.91 (14.58)        | 62.87 (14.01)       | 0.00      | 57.82 (13.70)        | 57.83 (13.31)       | 0.00      |
| Age categories without zero category                                              |                      |                     |           |                      |                     |           |                      |                     |           |                      |                     |           |
| ...18 - 54; n (%)                                                                 | 201 (41.0%)          | 184 (37.6%)         | 0.07      | 726 (52.6%)          | 748 (54.2%)         | -0.03     | 449 (26.4%)          | 453 (26.7%)         | -0.01     | 1,376 (38.5%)        | 1,385 (38.8%)       | -0.01     |
| ...55 - 64; n (%)                                                                 | 167 (34.1%)          | 170 (34.7%)         | -0.01     | 568 (41.1%)          | 547 (39.6%)         | 0.03      | 494 (29.1%)          | 475 (28.0%)         | 0.02      | 1,229 (34.4%)        | 1,192 (33.4%)       | 0.02      |
| ...65 - 74; n (%)                                                                 | 54 (11.0%)           | 87 (17.8%)          | -0.19     | 53 (3.8%)            | 48 (3.5%)           | 0.02      | 383 (22.5%)          | 427 (25.1%)         | -0.06     | 490 (13.7%)          | 562 (15.7%)         | -0.06     |
| ...>75; n (%)                                                                     | 68 (13.9%)           | 49 (10.0%)          | 0.12      | 34 (2.5%)            | 38 (2.8%)           | -0.02     | 373 (22.0%)          | 344 (20.2%)         | 0.04      | 475 (13.3%)          | 431 (12.1%)         | 0.04      |
| Gender without zero category- United                                              |                      |                     |           |                      |                     |           |                      |                     |           |                      |                     |           |
| ...Males; n (%)                                                                   | 240 (49.0%)          | 229 (46.7%)         | 0.05      | 727 (52.6%)          | 709 (51.3%)         | 0.03      | 786 (46.3%)          | 781 (46.0%)         | 0.01      | 1,753 (49.1%)        | 1,719 (48.2%)       | 0.02      |
| ...Females; n (%)                                                                 | 250 (51.0%)          | 261 (53.3%)         | -0.05     | 654 (47.4%)          | 672 (48.7%)         | -0.03     | 913 (53.7%)          | 918 (54.0%)         | -0.01     | 1,817 (50.9%)        | 1,851 (51.8%)       | -0.02     |
| Race                                                                              |                      |                     |           |                      |                     |           |                      |                     |           |                      |                     |           |
| ...White; n (%)                                                                   |                      |                     |           |                      |                     |           | 1,373 (80.8%)        | 1,381 (81.3%)       |           | 1,373 (80.8%)        | 1,381 (81.3%)       | 0.00      |
| ...Black; n (%)                                                                   |                      |                     |           |                      |                     |           | 247 (14.5%)          | 240 (14.1%)         |           | 247 (14.5%)          | 240 (14.1%)         | 0.00      |
| ...Asian; n (%)                                                                   |                      |                     |           |                      |                     |           | ** (0.5%)            | ** (0.4%)           |           | ** (0.5%)            | ** (0.4%)           | 0.00      |
| ...Hispanic; n (%)                                                                |                      |                     |           |                      |                     |           | 34 (2.0%)            | 33 (1.9%)           |           | 34 (2.0%)            | 33 (1.9%)           | 0.00      |
| ...North American Native; n (%)                                                   |                      |                     |           |                      |                     |           | ** (0.4%)            | ** (0.6%)           |           | ** (0.4%)            | ** (0.6%)           | 0.00      |
| ...Other/Unknown; n (%)                                                           |                      |                     |           |                      |                     |           | 29 (1.7%)            | 28 (1.6%)           |           | 29 (1.7%)            | 28 (1.6%)           | 0.00      |
| Region without zero category- United                                              |                      |                     |           |                      |                     |           |                      |                     |           |                      |                     |           |
| v3 (lumping missing+other category)                                               |                      |                     |           |                      |                     |           |                      |                     |           |                      |                     |           |
| ...Northeast; n (%)                                                               | 59 (12.0%)           | 66 (13.5%)          | -0.04     | 246 (17.8%)          | 232 (16.8%)         | 0.03      | 345 (20.3%)          | 339 (20.0%)         | 0.01      | 650 (18.2%)          | 637 (17.8%)         | 0.01      |
| ...South; n (%)                                                                   | 191 (39.0%)          | 187 (38.2%)         | 0.02      | 387 (28.0%)          | 397 (28.7%)         | -0.02     | 609 (35.8%)          | 608 (35.8%)         | 0.00      | 1,187 (33.2%)        | 1,192 (33.4%)       | 0.00      |
| ...Midwest; n (%)                                                                 | 137 (28.0%)          | 136 (27.8%)         | 0.00      | 527 (38.2%)          | 526 (38.1%)         | 0.00      | 442 (26.0%)          | 468 (27.5%)         | -0.03     | 1,106 (31.0%)        | 1,130 (31.7%)       | -0.02     |
| ...West; n (%)                                                                    | 103 (21.0%)          | 101 (20.6%)         | 0.01      | 218 (15.8%)          | 223 (16.1%)         | -0.01     | 303 (17.8%)          | 284 (16.7%)         | 0.03      | 624 (17.5%)          | 608 (17.0%)         | 0.01      |
| ...Unknown+missing; n (%)                                                         | N/A                  | N/A                 | #VALUE!   | ** (0.2%)            | ** (0.2%)           | 0.00      | N/A                  | N/A                 | #VALUE!   | ** (0.2%)            | ** (0.2%)           | 0.00      |
| CV Covariates                                                                     |                      |                     |           |                      |                     |           |                      |                     |           |                      |                     |           |
| Ischemic heart disease; n (%)                                                     | 90 (18.4%)           | 93 (19.0%)          | -0.02     | 186 (13.5%)          | 158 (11.4%)         | 0.06      | 373 (22.0%)          | 375 (22.1%)         | 0.00      | 649 (18.2%)          | 626 (17.5%)         | 0.02      |
| Acute MI; n (%)                                                                   | 23 (4.7%)            | 25 (5.1%)           | -0.02     | 64 (4.6%)            | 59 (4.3%)           | 0.01      | 81 (4.8%)            | 84 (4.9%)           | 0.00      | 168 (4.7%)           | 168 (4.7%)          | 0.00      |
| ACS/unstable angina; n (%)                                                        | 18 (3.7%)            | 17 (3.5%)           | 0.01      | 44 (3.2%)            | 35 (2.5%)           | 0.04      | 74 (4.4%)            | 69 (4.1%)           | 0.01      | 136 (3.8%)           | 121 (3.4%)          | 0.02      |
| Old MI; n (%)                                                                     | 18 (3.7%)            | 13 (2.7%)           | 0.06      | 16 (1.2%)            | 12 (0.9%)           | 0.03      | 89 (5.2%)            | 97 (5.7%)           | -0.02     | 123 (3.4%)           | 122 (3.4%)          | 0.00      |
| Stable angina; n (%)                                                              | ** (1.4%)            | ** (1.0%)           | 0.04      | 19 (1.4%)            | 16 (1.2%)           | 0.02      | 42 (2.5%)            | 43 (2.5%)           | 0.00      | #VALUE!              | #VALUE!             | #VALUE!   |
| Coronary atherosclerosis and other forms of chronic ischemic heart disease; n (%) | 62 (12.7%)           | 58 (11.8%)          | 0.03      | 104 (7.5%)           | 90 (6.5%)           | 0.04      | 266 (15.7%)          | 271 (16.0%)         | -0.01     | 432 (12.1%)          | 419 (11.7%)         | 0.01      |
| Other atherosclerosis with ICD10 v2                                               |                      |                     |           |                      |                     |           |                      |                     |           |                      |                     |           |
| Copy; n (%)                                                                       | ** (0.4%)            | ** (0.6%)           | -0.03     | ** (0.4%)            | ** (0.3%)           | 0.02      | 12 (0.7%)            | ** (0.6%)           | 0.01      | #VALUE!              | #VALUE!             | #VALUE!   |
| Previous cardiac procedure (CABG or PTCa or Stent) v4; n (%)                      | ** (0.4%)            | 0 (0.0%)            | 0.09      | ** (0.3%)            | ** (0.7%)           | -0.06     | ** (0.6%)            | ** (0.4%)           | 0.03      | #VALUE!              | #VALUE!             | #VALUE!   |
| History of CABG or PTCa; n (%)                                                    | 20 (4.1%)            | 14 (2.9%)           | 0.07      | ** (0.8%)            | ** (0.4%)           | 0.05      | 87 (5.1%)            | 96 (5.7%)           | -0.03     | #VALUE!              | #VALUE!             | #VALUE!   |
| Any stroke; n (%)                                                                 | ** (1.6%)            | ** (1.0%)           | 0.05      | 13 (0.9%)            | ** (0.8%)           | 0.01      | 58 (3.4%)            | 58 (3.4%)           | 0.00      | #VALUE!              | #VALUE!             | #VALUE!   |
| Ischemic stroke (w and w/o mention of cerebral infarction); n (%)                 | ** (1.6%)            | ** (1.0%)           | 0.05      | 13 (0.9%)            | ** (0.8%)           | 0.01      | 54 (3.2%)            | 56 (3.3%)           | -0.01     | #VALUE!              | #VALUE!             | #VALUE!   |
| Hemorrhagic stroke; n (%)                                                         | 0 (0.0%)             | 0 (0.0%)            | #DIV/0!   | 0 (0.0%)             | 0 (0.0%)            | #DIV/0!   | ** (0.2%)            | ** (0.1%)           | 0.03      | #VALUE!              | #VALUE!             | #VALUE!   |
| TIA; n (%)                                                                        | ** (0.4%)            | ** (0.4%)           | 0.00      | ** (0.2%)            | ** (0.2%)           | 0.00      | ** (0.6%)            | 13 (0.8%)           | -0.02     | #VALUE!              | #VALUE!             | #VALUE!   |
| Other cerebrovascular disease; n (%)                                              | ** (1.4%)            | ** (1.2%)           | 0.02      | ** (0.8%)            | ** (0.8%)           | 0.00      | 28 (1.6%)            | 30 (1.8%)           | -0.02     | #VALUE!              | #VALUE!             | #VALUE!   |
| Cerebrovascular procedure; n (%)                                                  | 0 (0.0%)             | 0 (0.0%)            | #DIV/0!   | 0 (0.0%)             | 0 (0.0%)            | #DIV/0!   | ** (0.1%)            | 0 (0.0%)            | 0.04      | #VALUE!              | 0 (0.0%)            | #VALUE!   |
| Heart failure (CHF); n (%)                                                        | 52 (10.6%)           | 53 (10.8%)          | -0.01     | 114 (8.3%)           | 115 (8.3%)          | 0.00      | 285 (16.8%)          | 304 (17.9%)         | -0.03     | 451 (12.6%)          | 472 (13.2%)         | -0.02     |
| Peripheral Vascular Disease (PVD) or PVD                                          |                      |                     |           |                      |                     |           |                      |                     |           |                      |                     |           |
| Surgery v2; n (%)                                                                 | 16 (3.3%)            | 15 (3.1%)           | 0.01      | 31 (2.2%)            | 32 (2.3%)           | -0.01     | 116 (6.5%)           | 111 (6.5%)          | 0.01      | 163 (4.6%)           | 158 (4.4%)          | 0.01      |
| Atrial fibrillation; n (%)                                                        | 36 (7.3%)            | 36 (7.3%)           | 0.00      | 90 (6.5%)            | 84 (6.1%)           | 0.02      | 178 (10.5%)          | 180 (10.6%)         | 0.00      | 304 (8.5%)           | 300 (8.4%)          | 0.00      |
| Other cardiac dysrhythmia; n (%)                                                  | 90 (18.4%)           | 90 (18.4%)          | 0.00      | 241 (17.5%)          | 234 (16.9%)         | 0.02      | 365 (21.5%)          | 379 (22.3%)         | -0.02     | 696 (19.5%)          | 703 (19.7%)         | -0.01     |
| Cardiac conduction disorders; n (%)                                               | 28 (5.7%)            | 28 (5.7%)           | 0.00      | 87 (6.3%)            | 68 (4.9%)           | 0.06      | 126 (7.4%)           | 127 (7.5%)          | 0.00      | 241 (6.8%)           | 223 (6.2%)          | 0.02      |
| Other CVD; n (%)                                                                  | 137 (28.0%)          | 132 (26.9%)         | 0.02      | 332 (24.0%)          | 359 (26.0%)         | -0.05     | 420 (24.7%)          | 450 (26.5%)         | -0.04     | 889 (24.9%)          | 941 (26.4%)         | -0.03     |
| Diabetes-related complications                                                    |                      |                     |           |                      |                     |           |                      |                     |           |                      |                     |           |
| Occurrence of Diabetic Neuropathy v2                                              |                      |                     |           |                      |                     |           |                      |                     |           |                      |                     |           |
| Copy; n (%)                                                                       | 18 (3.7%)            | 24 (4.9%)           | -0.06     | 26 (1.9%)            | 25 (1.8%)           | 0.01      | 100 (5.9%)           | 99 (5.8%)           | 0.00      | 144 (4.0%)           | 148 (4.1%)          | -0.01     |
| Occurrence of diabetic nephropathy V3 with ICD10 Copy; n (%)                      | 13 (2.7%)            | ** (1.2%)           | 0.11      | 18 (1.3%)            | 14 (1.0%)           | 0.03      | 47 (2.8%)            | 31 (1.8%)           | 0.07      | 78 (2.2%)            | #VALUE!             | #VALUE!   |
| Hypoglycemia v2; n (%)                                                            | ** (0.6%)            | ** (0.2%)           | 0.06      | ** (0.1%)            | 0.03                | 0.01      | 51 (3.0%)            | 44 (2.6%)           | 0.02      | #VALUE!              | #VALUE!             | #VALUE!   |
| Hyperglycemia; n (%)                                                              | 53 (10.8%)           | 41 (8.4%)           | 0.08      | 76 (5.5%)            | 80 (5.8%)           | -0.01     | 151 (8.9%)           | 158 (9.3%)          | -0.01     | 280 (7.8%)           | 279 (7.8%)          | 0.00      |
| Diabetic ketoacidosis; n (%)                                                      | ** (0.6%)            | ** (0.4%)           | 0.03      | ** (0.1%)            | ** (0.7%)           | -0.10     | ** (0.4%)            | ** (0.4%)           | 0.00      | #VALUE!              | #VALUE!             | #VALUE!   |
| Hypertension: 1 inpatient or 2 outpatient claims within 365 days; n (%)           | 207 (42.2%)          | 210 (42.9%)         | -0.01     | 553 (40.0%)          | 564 (40.8%)         | -0.02     | 775 (45.6%)          | 782 (46.0%)         | -0.01     | 1,535 (43.0%)        | 1,556 (43.6%)       | -0.01     |
| Hyperlipidemia v2; n (%)                                                          | 172 (35.1%)          | 171 (34.9%)         | 0.00      | 419 (30.3%)          | 405 (29.3%)         | 0.02      | 709 (41.7%)          | 710 (41.8%)         | 0.00      | 1,300 (36.4%)        | 1,286 (36.0%)       | 0.01      |
| Edema; n (%)                                                                      | 92 (18.8%)           | 74 (15.1%)          | 0.10      | 194 (14.0%)          | 188 (13.6%)         | 0.01      | 279 (16.4%)          | 281 (16.5%)         | 0.00      | 565 (15.8%)          | 543 (15.2%)         | 0.02      |
